11.2 Prior and Concomitant Medications

Prior medications are defined as medications that were stopped within the 3 months prior to Day 1; concomitant medications are defined as those medications ongoing at or started after Day 1. At the Screening Visit, subjects will be asked what medications they are taking, as well as those the subject may have taken but discontinued within the 3 months prior to Visit 1. At each study visit, subjects will be asked what concomitant medications they are currently taking or if there have been any changes to their medications since their first visit.

All prior and concomitant ocular and non-ocular medications will be listed including preferred name, indication, route of administration, start date, stop date, dosage, and frequency of administration. Prior and concomitant medications will be coded using the World Health Organization Drug Dictionary (WHODrug) Global, B3, September 2017 to the appropriate Anatomical Therapeutic Chemical (ATC) classification and WHO generic term.

Counts and percentages of ocular and non-ocular prior and concomitant medications will be summarized separately using ATC classification and preferred name. Summaries will include concomitant ocular medications for each eye (study eye and fellow eye), concomitant non-ocular medications, prior anti-VEGF ocular medications in the study eye, prior non-anti-VEGF ocular medications in the study eye, prior ocular medications in the fellow eye, and prior non-ocular medications. Summaries will be displayed by treatment group and over all subjects. Subjects with multiple medications in the same ATC class or preferred name will be counted only once for that respective ATC class or preferred name.

12. Dosing Compliance and Treatment Exposure

12.1 Dosing Compliance

Subjects who complete the study are scheduled to receive 4 injections [Visit 2 (Day 1), Visit 3 (Week 4), Visit 4 (Week 8), Visit 5 (Week 12)].

The number of masked injections, either KVD001 injection or a sham procedure, administered and the number of planned injections prior to study discontinuation will be summarized as counts and percentages in the SAF population. The number of planned injections is the number of masked injections that the subject would have taken if all scheduled visits occurred and injections were administered at all scheduled visits prior to discontinuation. If a rescue medication was administered at a visit, then that visit will not contribute to the planned injections.

Compliance will be calculated as

$$\text{Compliance (\%)} = 100 \times \frac{\text{Number of Masked Injections Received}}{\text{Number of Planned Injections}}$$

The number of masked injections administered and the number of planned injections prior to study discontinuation will be summarized as counts and percentages in the SAF Population. Dosing compliance (%) will be summarized with continuous descriptive statistics for each treatment group, using the SAF population.

Subject listings of study drug assignment, study drug administration, and study treatment compliance will also be produced.

12.2 Treatment Exposure

Treatment exposure will be measured by time-on-study, time from first injection to last injection, and time to last exposure to study treatment for the analysis of on-treatment AEs (time from first injection plus additional at-risk period following the last injection (the minimum of 28 days and time from last injection to last study visit)).

Time on study is defined as

$$\text{Time on Study (Days)} = [\text{Date of Last Visit} - \text{Date of Visit 2 (Day 1)}] + 1.$$

Time from first injection to last injection is defined as

$$\text{Time from First to Last Injection (Days)} = (\text{Date of Last Injection} - \text{Date of First Injection}) + 1.$$

Time to last exposure to study treatment for the analysis of on-treatment AEs is defined as

$$\text{Time Exposed (Days)} = (\text{Date of Last Injection} - \text{Date of First Injection}) + \text{ADT},$$

where ADT is the additional time exposed after the last injection and is evaluated as

$$ADT = \text{Minimum (28, Date of Last Visit – Date of Last Injection) + 1.}$$

Time on study, time from first injection to last injection, and time exposed for on-treatment adverse event analysis for each subject exposed to study drug will be summarized with continuous descriptive statistics (n, mean, SD, median, IQR, minimum, maximum) for each treatment group, using the SAF population. A subject listing of treatment exposure will also be produced.

[figure not shown]
13. Efficacy Analyses

[Redacted content]

13.1 Primary Analysis

The primary efficacy endpoint is change from baseline in BCVA letter count in the study eye at Week 16. Change from baseline in BCVA letter count will be calculated as Week 16 BCVA letter count minus Day 1 BCVA letter count such that a negative difference indicates a worsening in vision. In addition, treatment comparisons between each KVD001 Injection dose and the sham will be calculated as KVD001 Injection minus sham, such that a positive result indicates more letters gained in the KVD001 Injection treatment group. Treatment comparison between the KVD001 Injection doses will be calculated as KVD001 6 µg Injection minus KVD001 3 µg Injection, such that a positive result indicates more letters gained in the KVD001 6 µg Injection treatment group.

The study eye ETDRS letter scores including changes from baseline will be summarized using descriptive statistics for continuous variables. An analysis of covariance (ANCOVA) model will be used

to compare the change from baseline in BCVA letter count at Week 16 between each KVD001 Injection dose and the sham and between the KVD001 Injection doses.

Least-squares means (LSMeans) for each treatment group and its 95% CI will be presented. The LSMean difference between each KVD001 Injection dose and the sham and between the KVD001 Injection doses, their corresponding CIs, and the p-values will be presented.

[figure not shown]
Comparisons will use two-tailed, alpha=0.05 *t*-tests on the LSMean from the ANCOVA. LSMean for each treatment, the estimated treatment difference and the 95% CI for the difference will be calculated based on the ANCOVA model. An example of SAS® code implementation for changes from baseline in number of letters read correctly (using BCVA) is as follows:

[figure not shown]
```
proc mixed data=...;
  class ...;
  model ...;
  lsmeans ...;
run;
```

where

- | ...
- | ...
- | ...
- | ...

As a safeguard, the normality assumptions of the ANCOVA model used will be checked using a normal probability plot of the residuals and a plot of the residuals versus the fitted values (i.e., checking the normality assumption and the constant variance assumption of the model, respectively) to ensure that the model assumptions are reasonable. If there are any departures from the distributional assumptions, alternative methods of transformations may be explored.

13.2 Additional Analyses of the Primary Endpoint

An analysis using observed data only will also be performed in both the FAS and PPS. Additionally, multiple imputation methodology will be used to impute missing data in the FAS for the analysis of the primary efficacy variables.

[Redacted text block]

[Redacted text block]

[Redacted text block]

- | [Redacted list item]
- | [Redacted list item]
- | [Redacted list item]
- | [Redacted list item]
- | [Redacted list item]
- | [Redacted list item]

[figure not shown]
[Redacted text block]

[Redacted text block]

[Redacted text block]

[Redacted text block]

- | [Redacted list item]

- [REDACTED]
- | [REDACTED]
- | [REDACTED]
- | [REDACTED]
- | [REDACTED]
- | [REDACTED]
- | [REDACTED]
- | [REDACTED]
- | [REDACTED]

As a sensitivity analysis, treatment group differences for changes from baseline in BCVA letter count will be evaluated using a mixed model repeated measures (MMRM) ANCOVA fitted with treatment group, visit and the treatment by visit interaction as categorical variable terms with baseline BCVA letter score and baseline CST as covariates with contrasts included for each visit. LSMeans and 95% CIs for each treatment group, the LSMeans difference between each KVD001 Injection dose and the sham and between the KVD001 Injection doses, the corresponding CIs, and the p-values will be presented for each visit. The covariance matrix will be attempted first with an unstructured covariance matrix, then with autoregressive 1 if the unstructured is not estimable.

Subgroup analyses of the primary endpoint for the study stratification factors will be presented.

13.3 Secondary Analyses

The secondary endpoints are the following:

- Change from baseline in CST as measured by SD-OCT
- Proportion of eyes with a ≥ 2 step improvement from baseline in DRSS score
- Change from baseline in BCVA letter count as measured by ETDRS
- Proportion of SEs with ≥ 5 , ≥ 10 , and ≥ 15 BCVA letter gain from baseline and the proportion of SEs with ≥ 5 , ≥ 10 , and ≥ 15 BCVA letter loss from baseline.

Change from baseline in BCVA letter count as measured by ETDRS in the study eye and change from baseline in CST in the study eye as measured by the central image reading center (CIRC) using SD-OCT will be analyzed using the same method described for the primary efficacy analysis. Note that change from baseline in CST will be in favor of KVD001 if the treatment difference is < 0 .

The difference in proportion of SEs with improvement of 2 or more steps on the ETDRS DRSS score between each KVD001 injection dose and the sham and between the KVD001 Injection doses will be summarized by visit using discrete summary statistics, including 95% Clopper-Pearson CIs for each treatment group. The difference in proportions between each KVD001 Injection dose and the sham and between the KVD001 Injection doses will be analyzed using a Pearson's chi-squared test. 95% Clopper-

Pearson CIs for the differences in proportions will also be calculated. Fisher's exact tests and exact CIs will be employed in cases of expected counts <5.

The proportion of SEs with ≥ 5 , ≥ 10 and ≥ 15 BCVA letter change (gain and loss) between baseline and each post-baseline visit will be analyzed using the same method described for the proportion of SEs with improvement of 2 or more steps on the ETDRS DRSS score. Additionally, as an exploratory endpoint, the proportion of SEs with any BCVA letter loss between baseline and each post-baseline visit will be summarized similarly. Note that the categorizations of ≥ 5 , ≥ 10 and ≥ 15 BCVA letter change (gain and loss) or any BCVA letter loss are not mutually exclusive.

14. Safety Analyses

All safety data analyses will be performed on the safety population and displayed in subject data listings and summarized in tables. No statistical inferential testing will be performed for safety variables.

Safety endpoints include AEs, manifest refraction/BCVA, slip lamp biomicroscopy, dilated ophthalmoscopy, intraocular pressure (IOP), SD-OCT, EDTRS DRSS, physical exam findings, laboratory test results, and vital signs.

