8.5.1.2 Statistical Methods

The study eye ETDRS letter scores including changes from baseline will be summarized using continuous descriptive statistics. An analysis of covariance (ANCOVA) model will be used to compare the change from baseline in BCVA letter count at Week 16 between each dose of the KVD001 Injection and the sham. The ANCOVA model will include treatment as a main effect and baseline BCVA letter count as a covariate. Least-squares means (LSMeans) for each treatment group, the LSMean difference between each dose of the KVD001 Injection group and the sham group, the corresponding CIs and the p-values will be presented.

As a sensitivity analysis, treatment group differences for changes from baseline in BCVA letter count will be evaluated using a mixed model repeated measures (MMRM) ANCOVA fitted with treatment group, visit and the treatment by visit interaction as categorical variable terms with baseline BCVA letter score and baseline CST as covariates with contrasts included for each visit. LSMeans and 95% confidence intervals for each treatment group, the LSMeans difference between each dose of the KVD001 Injection and sham, the corresponding confidence intervals, and the p-values will be presented for each visit.

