8.5.2 Secondary Efficacy Analyses

The secondary efficacy endpoints are:

- Change from baseline in CST as measured by Spectral Domain OCT (SD-OCT)
- Proportion of eyes with a ≥ 2 step improvement from baseline in DRSS score
- Change from baseline in BCVA letter count as measured by ETDRS
- Proportion of study eyes with ≥ 5 , ≥ 10 , and ≥ 15 BCVA letter change from baseline (gain and loss).

Change from baseline in BCVA letter count in the study eye at Week 24 and change from baseline in CST in the study eye as measured by SD-OCT at Week 16 and Week 24 will be analyzed using the same method described for the primary efficacy analysis. Note that change from baseline in CST will be in favor of KVD001 if the treatment difference is < 0 .

The proportion of study eyes with improvement of 2 or more steps on the ETDRS DRSS score between the sham procedure group and each of the KVD001 injection groups will be summarized by visit using discrete summary statistics, including 95% asymptotic normal CIs for each treatment group. The difference in proportions between each of the KVD001 groups and the sham procedure group will be analyzed at Week 16 and Week 24 using a Pearson's chi-squared test. 95% asymptotic normal CIs for the differences in proportions will also be calculated. Fisher's exact tests and exact CIs will be employed in cases of expected counts < 5 .

The proportion of study eyes with ≥ 5 , ≥ 10 and ≥ 15 BCVA letter change (gain and loss) between baseline and Weeks 16 and 24 will be analyzed using the same method described for the proportion of study eyes with improvement of 2 or more steps on the ETDRS DRSS score.

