This SAP is being written with due consideration of the recommendations outlined in the most recent International Conference on Harmonisation (ICH) E9 Guideline entitled Guidance for Industry: Statistical Principles for Clinical Trials and the most recent ICH E3 Guideline, entitled Guidance for Industry: Structure and Content of Clinical Study Reports (CSR).

This SAP describes the data that will be analyzed and the subject characteristics, efficacy, safety and tolerability assessments that will be evaluated. This SAP provides details of the specific statistical methods that will be used. The statistical analysis methods presented in this document will supersede the statistical analysis methods described in the clinical protocol. If additional analyses are required to supplement the planned analyses described in this SAP, they may be completed and will be identified in the CSR.

2. Study Objectives

The primary objective of this study is to evaluate the efficacy of monthly dosing of intravitreal (IVT) injection of KVD001 in subjects with center-involving diabetic macular edema (ciDME) who have had prior anti-vascular endothelial growth factor (anti-VEGF) treatment. The secondary objective is to evaluate the local and systemic safety and tolerability of monthly dosing of KVD001 Injection in subjects with ciDME who have had prior anti-VEGF treatment.

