14.2.1.1.3	Analysis of Covariance of Change from Baseline in BCVA Letter Count in the Study Eye by CST Randomization Stratum and Visit	FAS Population ██████████
14.2.1.2	Analysis of Covariance of Change from Baseline in BCVA Letter Count in the Study Eye by Visit	FAS Population ██████████ ██████████
14.2.1.3.1	Analysis of Covariance of Change from Baseline in BCVA Letter Count in the Study Eye by Visit	FAS Population ██████ ██████████
14.2.1.3.2	Analysis of Covariance of Change from Baseline in BCVA Letter Count in the Study Eye by Visit	PPS Population ██████ ██████████
14.2.1.4	Mixed Model Repeated Measures Analysis of Covariance of Change from Baseline in BCVA Letter Count in the Study Eye by Visit	FAS Population ██████ ██████████
14.2.1.5.1	Proportion of Study Eyes with a ≥ 5 , ≥ 10 , and ≥ 15 BCVA Change from Baseline (Gain or Loss) by Visit	FAS Population ██████ ██████████
14.2.1.5.2	Proportion of Study Eyes with a ≥ 5 , ≥ 10 , and ≥ 15 BCVA Change from Baseline (Gain or Loss) by Visit	PPS Population ██████ ██████████
14.2.2.1	Analysis of Covariance of Change from Baseline in Central Subfield Thickness (μm) in the Study Eye by Visit	FAS Population ██████████
14.2.2.2	Analysis of Covariance of Change from Baseline in Central Subfield Thickness (μm) in the Study Eye by Visit	FAS Population ██████████ ██████████
14.2.2.3	Analysis of Covariance of Change from Baseline in Central Subfield Thickness (μm) in the Study Eye by Visit	FAS Population ██████ ██████████
14.2.2.4	Analysis of Covariance of Change from Baseline in Central Subfield Thickness (μm) in the Study Eye by Visit	PPS Population ██████ ██████████
14.2.2.5	Mixed Model Repeated Measures Analysis of Covariance of Change from Baseline in Central Subfield Thickness (μm) in the Study Eye by Visit	FAS Population ██████ ██████████
14.2.3.1	Proportion of Eyes with a ≥ 2 Step Improvement from Baseline in Diabetic Retinopathy Severity Scale Score by Visit	FAS Population ██████ ██████████
14.2.3.2	Proportion of Eyes with a ≥ 2 Step Improvement from Baseline in Diabetic Retinopathy Severity Scale Score by Visit	PPS Population ██████ ██████████
14.3.1.1.1	Overall Summary of Adverse Events (Ocular & Non-Ocular) by Treatment Group	SAF Population
14.3.1.1.2	Overall Summary of Adverse Events (Ocular) by Eye and Treatment Group	SAF Population
14.3.1.2.1	Treatment-Emergent Adverse Events by System Organ Class and Preferred Term	SAF Population

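### As far as it can be read, the plan adjusts change in CST for baseline BCVA; it should state that the CST ANCOVA uses baseline CST

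*SAP*

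**What the plan says.** Protocol 8.5.1.2 defines the primary analysis of change in BCVA at Week 16: "The ANCOVA model will include treatment as a main effect and baseline BCVA letter count as a covariate". The synopsis says the same. Protocol 8.5.2 then states that change in CST at Weeks 16 and 24 "will be analyzed using the same method described for the primary efficacy analysis". SAP 13.3 does likewise for CST as read by the central image reading center (CIRC): it "using SD-OCT will be analyzed using the same method described for the primary efficacy analysis". In both documents the only adaptation for CST is the sign: a negative treatment difference favors KVD001.

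SAP Section 1 gives the SAP precedence: "The statistical analysis methods presented in this document will supersede the statistical analysis methods described in the clinical protocol". SAP 13.1 names an ANCOVA "to compare the change from baseline in BCVA letter count at Week 16 between each KVD001 Injection dose and the sham", but its model statement and variable list are blacked out in the public copy.

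Baseline CST appears in two other places. The sensitivity MMRM for BCVA in SAP 13.2 is fitted "with baseline BCVA letter score and baseline CST as covariates". Randomization is stratified by CST at 450 µm (Protocol Section 8; SAP Section 4 and 4.1). SAP Section 19 also lists, as Table 14.2.2.5, a "Mixed Model Repeated Measures Analysis of Covariance of Change from Baseline in Central Subfield Thickness", without restating its covariates.

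**The concern.** In an ANCOVA of a change score, the covariate that matters most is usually the baseline of the variable being analyzed. A thick retina at Day 1 has more room to thin and tends to regress more. Baseline letters read can capture that only through their correlation with thickness. A programmer who carried the protocol's covariate over unchanged would adjust CST for a different variable's baseline.

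CST is the first-listed secondary endpoint and the anatomical evidence for the proposed mechanism. Two things are at stake. One is precision: the residual variance is larger than it need be. The other is a conditional shift: if one arm happens to start thicker, part of that difference stays in the estimate for this trial.

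**Working it through.** **Inputs.** From the documents: 41 subjects per arm, 1:1:1 allocation, and stratification at 55 letters and 450 µm. The plan gives no figure for CST to reproduce. Its one power statement concerns BCVA (5 letters, SD 7.5, two-sided 0.05, approximately 80%). An exact t calculation gives 84.7% with 41 per arm, which is conservative and does not bear on this point. The documents give no CST standard deviation or correlation, so the following are assumptions:

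- r, the correlation of baseline with Week 16 CST: 0.5 to 0.7, with 0.3 and 0.8 to show the range;
- q, the correlation of baseline BCVA with baseline CST: −0.3 to −0.5;
- equal CST variance s² at both times, with s = 100 µm where a scale is needed;
- BCVA related to later CST only through baseline CST.

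**Step 1: residual variance of CST change.**

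- No covariate: 2(1 − r)s²
- Baseline BCVA: [2(1 − r) − q²(1 − r)²]s²
- Baseline CST: (1 − r²)s²
- Ratio, CST model to BCVA model: (1 + r) / [2 − q²(1 − r)]

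For r = 0.5 and q = −0.3 the ratio is 1.5 / (2 − 0.045) = 0.767, and √0.767 = 0.876, so the model-based SE is 12% lower.

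| r | q | Variance ratio | Model-based SE lower by |
|---|---|---|---|
| 0.3 | −0.3 | 0.671 | 18% |
| 0.5 | −0.3 | 0.767 | 12% |
| 0.5 | −0.5 | 0.800 | 11% |
| 0.7 | −0.3 | 0.862 | 7% |
| 0.7 | −0.5 | 0.883 | 6% |
| 0.8 | −0.3 | 0.908 | 5% |
| 0.8 | −0.5 | 0.923 | 4% |

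**Step 2: effect of stratification on the true sampling error.** A simulation used 123 subjects, 4,000 replicates, s = 100 µm and q = −0.3. Allocation was by blocks of six in four strata, cut at the medians. The stratifying CST reading was correlated 0.95 with the Day 1 value.

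| r | SE, BCVA covariate | SE, CST covariate | Ratio | Lower by |
|---|---|---|---|---|
| 0.3 | 23.44 | 21.00 | 1.12 | 10% |
| 0.5 | 20.71 | 19.25 | 1.08 | 7% |
| 0.7 | 16.46 | 15.91 | 1.03 | 3% |

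All SEs are in µm. Stratification has already taken up part of the gain.

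**Step 3: the reported interval.** The model-based SE comes from the residual variance and does not see the stratification. At r = 0.5 and q = −0.3, the BCVA model would report about 100 × √(0.978 × 2/41) = 21.8 µm against a true 20.7 µm. The CST model would report about 100 × √(0.75 × 2/41) = 19.1 µm against a true 19.3 µm. Stratifying on CST without adjusting for it therefore overstates the uncertainty.

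**Step 4: chance imbalance.** The SD of the between-arm difference in baseline CST is 100 × √(2/41) = 22 µm without stratification and about 15 µm with it (simulated). About (1 − r) of an imbalance stays in the estimate when baseline CST is not in the model. A one-SD imbalance under stratification thus carries about 0.5 × 14.5 = 7 µm at r = 0.5, and 0.3 × 14.6 = 4 µm at r = 0.7.

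**The case against.** The strongest objection is that the SAP governs and its model cannot be read. The protocol's covariate sentence is not repeated in the readable part of SAP 13.1. The hidden terms may include baseline CST, or a generic term for the baseline of the analyzed variable. The SAP code is offered as an example for BCVA letters, which suggests adaptation for other endpoints, and applying the same method to CST can naturally mean the same model form with its own baseline. SAP Section 16 lists no change of covariates, but that list is not complete: it also omits the 28-day limit on treatment-emergent events (SAP 14.1 against Protocol 8.6.1) and the categorical DRSS summary (SAP 14.4 against Protocol 8.6.10). This objection stands. A reader might infer that the plan demonstrably omits baseline CST; the documents do not support that, and blacked-out text is not a gap in the plan.

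Three further objections stand in part:

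- **Stratification by CST** removes about a third of the SD of chance imbalance (22 to 15 µm). It does not remove all of it. The factor is a two-level split of the study center's reading, placed at Screening in Protocol Section 8 and SAP Section 4 but at Day 1 in Protocol 4.5.2 and SAP 3.1, whereas the endpoint is the CIRC reading.
- **The CST MMRM** would include baseline CST if it uses the covariates given in SAP 13.2 for BCVA. The SAP does not say so, and the MMRM does not alter the ANCOVA in Tables 14.2.2.1 to 14.2.2.4.
- **The size of the gain is assumed.** If r = 0.8 and the follow-up SD is 1.25 times the baseline SD, the slope of change on baseline is 0.8 × 1.25 − 1 = 0 and the gain vanishes. At r = 0.3 it is larger than the main range.

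**Conclusion.** On the readable text taken literally, change in CST is adjusted for baseline BCVA and not for baseline CST. Whether the governing SAP model does this cannot be determined from the public copy. If it does, the cost is a model-based SE that baseline CST would lower by about 6% to 12%, and a true sampling error that it would lower by about 3% to 7% given stratification. These figures assume r of 0.5 to 0.7 and equal variances, with q of −0.3 to −0.5 for the first and −0.3 for the second. The gain is smaller at higher correlations.

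A reader might also infer that the CST estimate is biased. It is not: randomization keeps it unbiased on average. The harm is lost precision and a conditional shift in a trial where the arms happen to differ at Day 1. CST is an unpowered secondary endpoint in an exploratory study, and the primary BCVA analysis is not affected. This is a free improvement, not a demonstrated analysis error.

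**What to change.** In SAP 13.3 and Protocol 8.5.2, state that change from baseline in CST is analyzed by ANCOVA with treatment as a main effect and baseline CIRC-read CST as covariate. Apply this to Tables 14.2.2.1 to 14.2.2.4. State also that the CST MMRM in Table 14.2.2.5 includes baseline CST. Baseline BCVA is not needed as a second covariate on these assumptions: at r = 0.5 with stratification, the simulated SE was 19.28 µm with both and 19.25 µm with CST alone.

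If the blacked-out model already holds baseline CST, only the wording needs to change. Otherwise the cost is one sentence in each document and one covariate in the program, settled before unmasking. The baseline CST value is already collected, so no new data are needed.
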